1. INTRODUCTION

The purpose of this Statistical Analysis Plan (SAP) is to describe the final planned analyses to be included in the Clinical Study Report (CSR) for Study 209348, and to describe the analyses to be performed for the pre-specified interim analysis, which will be used in early Commit to Phase 3 (C2P3) decision making.

1.1. Objectives, Estimands and Endpoints

Study 209348 is intended to evaluate whether up to 24 weeks of treatment with GSK3228836 followed by up to 24 weeks of pegylated interferon (PegIFN) can increase the rate of hepatitis B virus surface antigen (HBsAg) loss in participants on stable nucleos(t)ide analogue (NA) therapy, and whether virologic response can be sustained once PegIFN treatment is discontinued. Study 209348 will also evaluate the safety and tolerability of the treatment regimen. In addition, pharmacokinetic, virology, and biomarker assessments will be evaluated for exploratory purposes.

Objectives and Estimands:

Objectives	Estimands and Endpoints
Primary	

Efficacy: To investigate the efficacy of two different durations of GSK3228836 followed by up to 24 weeks of PegIFN therapy in participants with CHB on stable NA therapy.
	
The main Estimand supporting the primary objective is defined as:
 
 • Population: Participants with CHB on stable NA therapy • Treatment: 300 mg GSK3228836 for 12 or 24 weeks followed by up to 24 weeks of PegIFN therapy while on stable NA therapy • Variable (Categorical): Participants achieving Sustained Virologic Response (SVR) (HBsAg <LLOQ and HBV DNA <LLOQ) for 24 weeks after the planned end of sequential treatment, without use of any rescue medication • Intercurrent Events: 
 ○ Discontinuation of, interruption in, and non-adherence to GSK3228836 and PegIFN not related to any wide disruptive events (such as COVID-19 pandemic) will be ignored (treatment policy strategy). ○ Ineligibility to receive PegIFN will be ignored (treatment policy strategy) ○ Use of rescue medication (composite strategy). ○ Wide disruptive events (such as COVID-19 pandemic) leading to discontinuation of, interruption in, and non-adherence to GSK3228836 and PegIFN will be handled assuming they had not happened (hypothetical strategy). • Population Summary: The percentage of participants in each treatment group who achieve SVR, without use of any rescue medication

Objectives	Estimands and Endpoints
	
The main primary estimand supporting the primary objective in participants with CHB on stable NA therapy in each treatment arm is the percentage of participants that achieve SVR (HBsAg <LLOQ and HBV DNA <LLOQ) for 24 weeks after the planned end of sequential treatment in the absence of rescue medication, regardless of ineligibility to receive PegIFN, discontinuation of, interruption in, and non-adherence to GSK3228836 and PegIFN, had they not been affected by wide disruptive events.
 
Three supplementary Estimands are defined to support the primary objective:
 
 • The first supplementary Estimand is defined in the same way as the main Estimand, except the assessment time frame for patients achieving SVR will be 24 weeks after the actual end of treatment. Therefore, the strategy for intercurrent events of treatment discontinuation will be while-on-treatment. This supplementary estimand supporting the primary objective in participants with CHB on stable NA therapy in each treatment arm is the percentage of participants that achieve SVR (HBsAg <LLOQ and HBV DNA <LLOQ) for 24 weeks after the actual end of sequential treatment in the absence of rescue medication, regardless of ineligibility to receive PegIFN, discontinuation of, interruption in, and non-adherence to GSK3228836 and PegIFN, had they not been affected by wide disruptive events. • The second supplementary Estimand is to understand the relationship between the PegIFN duration and achieving SVR for 24 weeks after the actual end of treatment, defined as: 
 ○ Population: Participants with CHB on stable NA therapy ○ Treatment: 300 mg GSK3228836 for 12 or 24 weeks followed by 24 weeks of PegIFN therapy while on stable NA therapy ○ Variable: The relationship between SVR for 24 weeks after actual end of treatment and the duration of PegIFN received by participants ○ Intercurrent Events: 
 ▪ Discontinuation and delayed start of, PegIFN, will be accounted to reflect the actual duration from the first to the last dose of PegIFN received (while-on-treatment strategy).

Objectives	Estimands and Endpoints
	
 ▪ Interruption in and other non-adherence to PegIFN will be ignored (treatment policy strategy) ▪ Discontinuation of, interruption in and non-adherence to GSK3228836 will be ignored (treatment policy strategy) ▪ Use of rescue medication (composite strategy). ▪ Wide disruptive events (such as COVID-19 pandemic) leading to discontinuation and delayed start of, PegIFN will be handled with while-on-treatment strategy; wide disruptive events leading to interruption in and other non-adherence to PegIFN will be ignored (treatment policy strategy); wide disruptive events leading to discontinuation of, interruption in, and non-adherence to GSK3228836 will be ignored (treatment policy strategy). ○ Population Summary: The percentage of participants achieving SVR for 24 weeks after the actual end of treatment by PegIFN treatment duration categorical grouping in each treatment arm • The second supplementary Estimand (supporting the primary objective in participants with CHB on stable NA therapy) is the percentage of participants achieving SVR for 24 weeks after the actual end of treatment by PegIFN treatment duration categorical grouping in each treatment arm, taking into account discontinuation and delayed start of PegIFN, regardless of interruption in and other non-adherence to PegIFN, regardless of discontinuation of, interruption in and non-adherence to GSK3228836. • The third supplementary Estimand is defined in the same way as the main Estimand, except the strategy for intercurrent events of PegIFN ineligibility for more than 12 weeks and/or missing more than 12 doses of PegIFN will be principal stratum. This supplementary Estimand supporting the primary objective is the percentage of participants in each treatment arm that achieve SVR (HBsAg <LLOQ and HBV DNA <LLOQ) for 24 weeks after the planned end of sequential treatment in participants with CHB on stable NA therapy and receiving at least 12 doses of PegIFN, in the absence of rescue medication, regardless of discontinuation of, interruptions in or non-adherence to GSK3228836

Objectives	Estimands and Endpoints
	had they not been affected by wide disruptive events.

1.2. Study Design

Overview of Study Design and Key Features	

The diagram illustrates the study design for two treatment arms, each with N=50 participants. Both arms start with 'Continuation of Nucleos(t)ide Therapy' from Week 0 to Week 72. Arm 1 receives 'GSK-836 - 24 Wks' from Week 0 to Week 24, followed by 'PEG-IFN' from Week 24 to Week 48, and 'OFF TREATMENT' from Week 48 to Week 72. Arm 2 receives 'GSK-836 - 12 Wks' from Week 0 to Week 12, followed by 'PEG-IFN' from Week 12 to Week 48, and 'OFF TREATMENT' from Week 48 to Week 72. A legend indicates that the dotted area represents Peg-IFN treatment initiation only after patient eligibility is confirmed, and a star marks the primary endpoint at 24 weeks off-treatment.
	
Design Features	
 Phase IIb, multi-center, randomised, open label study to assess the efficacy and safety of sequential treatment with GSK3228836 followed by Pegylated Interferon Alpha 2a in participants with CHB while on stable nucleos(t)ide treatment.
Study Intervention	
 Arm 1: 300 mg GSK3228836 once/week for 24 weeks (plus loading doses of 300 mg GSK3228836 on Day 4 and Day 11) followed by PegIFN (180 mcg/week for up to 24 weeks). Arm 2: 300 mg GSK3228836 once/week for 12 weeks (plus loading doses of 300 mg GSK3228836 on Day 4 and Day 11) followed by PegIFN (180 mcg/week for up to 24 weeks).
Study Intervention Assignment	
 Participants will be randomised in a 1:1 ratio to receive study intervention. Approximately 100 participants are planned to be enrolled in the study. The study team may enrol additional participants to within 10% of the planned 100.
Interim Analyses	
 Administrative Interim analyses: interim analyses to support internal decision making at multiple timepoints throughout the study. Planned efficacy Interim analysis: all participants complete the end-of-treatment visit and a sufficient number of participants complete off-treatment follow-up in order to assess the probability of C2P3. Independent Data Monitoring Committee (IDMC) safety review: approximately every 3 months.

1.2. Study Design

Overview of Study Design and Key Features	

The diagram illustrates the study design for two treatment arms, each with N=50 participants. Both arms start with 'Continuation of Nucleos(t)ide Therapy' from Week 0 to Week 72. Arm 1 receives 'GSK-836 - 24 Wks' from Week 0 to Week 24, followed by 'PEG-IFN' from Week 24 to Week 48, and 'OFF TREATMENT' from Week 48 to Week 72. Arm 2 receives 'GSK-836 - 12 Wks' from Week 0 to Week 12, followed by 'PEG-IFN' from Week 12 to Week 48, and 'OFF TREATMENT' from Week 48 to Week 72. A primary endpoint is marked with a star at Week 60 for both arms. A legend explains that the dotted area represents PEG-IFN treatment initiation only after patient eligibility is confirmed, and the star indicates the primary endpoint at 24 weeks off-treatment.
	
Design Features	
 Phase IIb, multi-center, randomised, open label study to assess the efficacy and safety of sequential treatment with GSK3228836 followed by Pegylated Interferon Alpha 2a in participants with CHB while on stable nucleos(t)ide treatment.
Study Intervention	
 Arm 1: 300 mg GSK3228836 once/week for 24 weeks (plus loading doses of 300 mg GSK3228836 on Day 4 and Day 11) followed by PegIFN (180 mcg/week for up to 24 weeks). Arm 2: 300 mg GSK3228836 once/week for 12 weeks (plus loading doses of 300 mg GSK3228836 on Day 4 and Day 11) followed by PegIFN (180 mcg/week for up to 24 weeks).
Study Intervention Assignment	
 Participants will be randomised in a 1:1 ratio to receive study intervention. Approximately 100 participants are planned to be enrolled in the study. The study team may enrol additional participants to within 10% of the planned 100.
Interim Analyses	
 Administrative Interim analyses: interim analyses to support internal decision making at multiple timepoints throughout the study. Planned efficacy Interim analysis: all participants complete the end-of-treatment visit and a sufficient number of participants complete off-treatment follow-up in order to assess the probability of C2P3. Independent Data Monitoring Committee (IDMC) safety review: approximately every 3 months.

2. STATISTICAL HYPOTHESES

The primary objective of the study is to investigate the effectiveness of GSK3228836 and PegIFN sequential therapy in CHB participants on stable NA therapy. The primary endpoint is achieving a sustained virologic response (SVR, HBsAg <LLOQ and HBV DNA <LLOQ) for 24 weeks after the planned end of GSK3228836 and PegIFN sequential treatment in the absence of rescue medication. Rescue medication is defined as any medication initiated for the purpose of antiviral suppression other than the background stable NA therapy.

A secondary objective is to compare the efficacy between 24 and 12 weeks of GSK3228836 treatment followed by PegIFN for up to 24 weeks, measured by the proportion of participants that achieve virologic response at the planned end of sequential treatment and sustained for six months or more post-treatment. The aim of the study is to provide evidence for efficacy of GSK3228836 and PegIFN sequential therapy in reaching sustained virologic response, and to inform selection of treatment regimen for Phase III trials based on the comparison between the two arms.

The primary aim for the study is descriptive, hence no formal hypothesis testing is planned. A probability inference approach will be used for decision-making. The primary assessment of interest is the SVR rate of each treatment group. The point estimates for SVR and 95% credible intervals will be calculated using a Bayesian probability approach. In addition, posterior probabilities that the true SVR in each treatment arm is greater than a range of clinically meaningful response rates will be provided.

Comparisons between treatment arms as defined in the key secondary objectives will be assessed using probability inference approaches.

2.1. Multiplicity Adjustment

No adjustments will be made for multiplicity.

3. ANALYSIS SETS

The following populations are defined for the analyses:

Analysis Set	Definition / Criteria	Analyses Evaluated
Screened	
 All participants who were screened for eligibility. 	Study Population
Enrolled	
 All participants who passed screening (met eligibility criteria) and entered the study. Note screening failures (who never passed screening even if rescreened) and participants screened but never enrolled into the study are excluded from the Enrolled population as they did not enter the study. 	Study Population
ITT	
 All randomised participants. This population will be based on the treatment the participant was randomised to. Any participant who receives a treatment randomisation number will be considered to have been randomised. 	Efficacy
Safety	
 All participants who were randomised and received at least one dose of study treatment. This population will be based on the treatment the participant received. Note: Participants who were not randomised but received at least one dose of study treatment will be listed. 	Safety Virology
Pharmacokinetic (PK)	
 All participants in the Safety population who received an active study treatment and had at least 1 non-missing PK assessment (Non-quantifiable [NQ] values will be considered as non-missing values) Note: PK samples that may be affected by protocol deviations will be reviewed by the study team to determine whether the sample will be excluded. 	PK
Pharmacodynamic (PD)	
 All participants in the Safety population for whom a Pharmacodynamic sample was obtained and analysed. 	PD

4. STATISTICAL ANALYSES

4.1. General Considerations

All analyses will be performed based on the population of participants with CHB on stable nucleos(t)ide therapy.

The following definitions and abbreviations will be used throughout to define time points for key efficacy endpoints and estimand criteria:

Time point	Definition	Abbreviation
End of treatment	End of sequential treatment of GSK3228836 and Peginterferon. Time point is expected at week 48/36 for Arm 1/Arm 2.	EoT
End of off-treatment follow-up after end of treatment	End of 24 weeks of off-treatment follow-up after end of treatment. Time point is expected at week 72/60 for Arm 1/Arm 2	EoT+24wks
End of study	Final scheduled assessment visit. Time point is expected at week 72 for Arm 1/Arm 2	EoS

The following definitions and abbreviations will be used to define reporting of scheduled efficacy visits:

Time point	Definition	Abbreviation
Scheduled End of GSK3228836 and PegIFN Sequential Treatment	Scheduled visit Week 48 in Arm 1 and Scheduled visit Week 36 in Arm 2.	PegIFN W36/W48
Scheduled End of 24 Weeks after Sequential Treatment	Scheduled visit Week 72 in Arm 1 and Scheduled visit Week 60 in Arm 2.	OT-W24

4.1.1. General Methodology

Participants who prematurely withdrew from study will not be replaced.

In the case of incorrect randomization stratification assignment at the time of randomization, the analyses will be performed based on the actual stratum per data collected in the baseline lab electronic Case Report Form (eCRF). In the case of randomization to the incorrect strata (i.e., if a HBsAg subject is randomised to the HBeAg strata, or vice versa), analysis will be performed based on the actual strata the subject should have been assigned to.

Unless otherwise specified, continuous data will be summarized using descriptive statistics: n, mean, standard deviation (std), median, minimum, and maximum. Categorical data will be summarized as the number and percentage of participants in each category.

Unless otherwise specified, CIs will use 95% confidence levels.

HBV DNA, HBsAg and HBeAg levels below the LLOQ will be imputed for summaries of actual values and change from baseline. The numeric values for HBV DNA <LLOQ (LLOQ=20 IU/mL) will be imputed as 19.9. The numeric values for HBsAg <LLOQ (LLOQ=0.05 IU/mL) will be imputed as 0.04. The numeric values for HBeAg <LLOQ (LLOQ=0.06 U/mL) will be imputed as 0.05.”

HBV DNA (IU/mL) and HBV RNA (copies/mL) levels that are “TND” will be imputed as 1. HBcrAg (Log₁₀ U/mL) values that are “TND” will be imputed as 0. Values <LLOQ are imputed based on the number of significant digits, similar to other lab parameters.

4.1.2. Baseline Definition

For all endpoints (except as noted in baseline definitions) the baseline value will be the latest pre-dose assessment with a non-missing value, including those from unscheduled visits. If time is not collected, Day 1 assessments are assumed to be taken prior to first dose and used as baseline. If there are multiple assessments collected at the same scheduled time, the average of these assessments will be used as the baseline.

Unless otherwise stated, if baseline data is missing no derivation will be performed and baseline will be set to missing.

Baseline of estimated glomerular filtration rate (eGFR) is defined as the mean of all pre-dose values, from screening to Day 1 pre-dose assessment.

4.1.3. Relapse Definition

One way to illustrate response durability and the benefit of adding PegIFN sequential therapy is to consider time to relapse among Bepi and/or PegIFN End of Treatment (EOT) responders. Time to relapse from end of Bepi treatment will be calculated using the Bepirovirsen EOT window with the following limits referred to in Section 4.2.2.1.

Only participants who were virologic responders at the end of Bepirovirsen EOT (See Section 4.2.2.1 windowing rules) without any prior rescue medication will be considered.

The start date used to measure the time to relapse will be the date of the first visit in the appropriate window where the participant is a responder and remains a responder at all subsequent visits within the window. Response and relapse rates can be evaluated under the conservative and modified definition of SVR.

Discontinuation interruption in, or non-adherence to GSK3228836 and PegIFN related or unrelated to wide disruptive events (WDEs) will be analysed as collected when determining relapse (treatment policy strategy).

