4.1.3.1. Relapse under Conservative Definition (SVR)

Relapse date is defined as the first visit after the appropriate window end date where observed data for either HBsAg or HBV DNA is greater than the lower limit of quantification (LLOQ) or the use of rescue medication.

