4.2.2.1. Visit Windowing and Multiple Measurements at One Analysis Timepoint

Visit windowing for the primary end-point will be applied as specified in [Table 2](#) and [Table 3](#), and the windowed results will be used to determine the primary endpoint of SVR. Unscheduled assessments will be included in the analysis window. No imputation of missing data will be performed prior to visit windowing.

If there are multiple values within an analysis window the following rules will be applied:

For the end of GSK3228836 treatment and PegIFN treatment analysis timepoints, the latest available assessment in the window will be selected, with the worst non-missing value chosen first. The worst case ordering is as follows:

1. No Virologic Response
2. Missing due to WDE¹
3. Virologic Response
4. Missing (unrelated to WDEs)

For post end of sequential treatment analysis timepoints:

1. Worst non-missing value in the analysis window will be selected.
 - a) If values are the same, then the value closest to target day will be selected. If there are multiple values equidistant from the target day, the earliest will be selected.
 - b) If all values within an analysis window are missing, then the result is missing for the analysis window.
2. Worst value is defined in the order of highest actual value, then <LLOQ, and then TND.

¹ Missing due to WDE will be considered based on whether original value for the assessment is missing or is a non-response. If the original value at an assessment is 'No Virologic Response' prior to imputation for WDEs, then the assessment will be classified as 'Missing due to WDEs'. If the original value at an assessment is 'Missing' prior to imputation for WDEs, then the preceding non-missing value within the window will be selected.

Table 2 Primary Endpoint Analysis Visit Windows for Arm 1

Analysis Set	Parameter	Target Study Day	Analysis Window		Analysis Timepoint	Protocol Visit
			Beginning Timepoint	Ending Timepoint		
Efficacy	HBsAg and HBV DNA	162	148	Minimum of (182, PegIFN First Dosing Study day)	End of GSK3228836 treatment	Week 24
Efficacy	HBsAg and HBV DNA	330	295	350	End of PegIFN treatment / EoT	Week 48
Efficacy	HBsAg and HBV DNA	386	351	406	Post PegIFN treatment Week 8	Off-treatment Week 8
Efficacy	HBsAg and HBV DNA	456	407	462	Post PegIFN treatment Week 18	Off-treatment Week 18
Efficacy	HBsAg and HBV DNA	498	463	518	Post PegIFN treatment Week 24	Off-treatment Week 24

Table 3 Primary Endpoint Analysis Visit Windows for Arm 2

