Population summary: summary statistics of the time from Bepirovirsen end of treatment to relapse including: N(%) with relapse, mean, standard deviation, median, minimum, and maximum using the number of participants achieving VR at Bepi EOT. Additionally, a Kaplan-Meier plot and associated percentiles will be produced to provide a graphical comparison of time to relapse between treatment arms.

Only participants who were virologic responders at the end of Bepirovirsen treatment will be considered, since they are the only ones who can relapse. Time to relapse is defined as the first time point where the participant can no longer be considered a responder by the primary estimand for the conservative definition. This includes observed elevation(s) in either HBsAg or HBV DNA or rescue medication usage. Generally, time from end of Bepirovirsen treatment to relapse will be calculated from the date of the planned Week 24 or 12 visit (for arms 1 and 2 respectively), where HBsAg<LLOQ and HBV DNA<LLOQ,

until the first visit after the planned Week 24 or 12 visit where HBsAg \geq LLOQ or HBV DNA \geq LLOQ.

4.3.1.2. Durability of Virological Response after Sequential Therapy with 12 Weeks of GSK3228836 Followed by up to 24 Weeks of PegIFN

The estimand strategy supporting this secondary objective is the same strategy defined in Section 4.3.1.1 and focuses on the timepoints following the 24 weeks off-treatment period(i.e., Week 30 and Week 36).

4.3.1.3. Comparison of Efficacy Between Treatment Arms of 12 and 24 Weeks of GSK3228836 Followed by up to 24 Weeks of PegIFN

The estimand strategy for this objective are defined as follows:

- **Population:** Participants with CHB on stable NA therapy, regardless of discontinuation of, interruptions in or adherence to GSK3228836 or PegIFN, had they not been affected by wide disruptive events.
- **Treatment:** 300 mg GSK3228836 for 12 or 24 weeks followed by up to 24 weeks of PegIFN therapy while on stable NA therapy. One treatment comparison between Arms 1 and 2 up to 24 weeks off treatment.

- **Intercurrent Events:**
 - Discontinuation of, interruption in, and non-adherence to GSK3228836 and PegIFN will be analysed as collected (treatment policy).
 - PegIFN ineligibility will be analysed as collected (treatment policy)
 - Participants who have used rescue medication will be incorporated in the definition of the endpoint (composite strategy)

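### Time from bepirovirsen end of treatment to relapse has two incompatible definitions in the SAP, and one builds in event-free time that varies with PegIFN start

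*SAP*

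**What the plan says.** **SAP 4.1.3 and 4.1.3.1.** The window is fixed first: "Time to relapse from end of Bepi treatment will be calculated using the Bepirovirsen EOT window with the following limits referred to in Section 4.2.2.1". On the origin: "The start date used to measure the time to relapse will be the date of the first visit in the appropriate window", with the condition that the participant "remains a responder at all subsequent visits within the window". On the event: "Relapse date is defined as the first visit after the appropriate window end date where observed data for either HBsAg or HBV DNA" exceeds the limit, or rescue medication is used. The threshold is that the value "is greater than the lower limit of quantification (LLOQ").

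**SAP 4.2.2.1, Tables 2 and 3.** The end-of-GSK3228836 window opens on Day 148 in Arm 1 and closes at "Minimum of (182, PegIFN First Dosing Study day"). In Arm 2 it opens on Day 64 and closes on Day 98 or the first PegIFN dosing day, whichever is earlier. Target days are 162 and 78. Where the window holds several values, the latest available assessment decides response at this timepoint.

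**SAP 4.3.1.1, time-to-event variables.** Time to relapse "will be calculated from the date of the planned Week 24 or 12 visit (for arms 1 and 2 respectively") to the first visit after that planned visit with HBsAg or HBV DNA at or above LLOQ. Window end is not mentioned. The analysis is limited to virologic responders at the end of bepirovirsen treatment. It is reported as summary statistics and a Kaplan-Meier plot by arm, and its stated purpose is to show whether adding PegIFN delays relapse.

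**The concern.** The two sections describe one endpoint but differ in origin, in the first visit that can count as an event, and in the threshold. The SAP does not say which governs. According to the SAP version history, version 4.0 added both the relapse definitions in 4.1.3 and the endpoint in 4.3.1.1, so neither reads as a leftover from an older plan.

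Section 4.1.3 has a further problem. It starts the clock inside a window in which relapse cannot occur by definition, and that window closes when PegIFN starts. Guaranteed event-free time therefore depends on the timing of the treatment whose effect on relapse is in question. Two programmers following the two sections could produce different relapse counts, cohorts and Kaplan-Meier curves from the same data.

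**Working it through.** **Inputs.** Window limits come from SAP Tables 2 and 3, and nominal visit days from the formulas in SAP Table 19. Protocol Table 4 places the first planned PegIFN visit 7 days after the planned GSK3228836 dosing period. Protocol 4.1 allows PegIFN to start up to 12 weeks late, or not at all.

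**Reproducing the plan's days.** Target day = 1 + 7 × (week − 1).
- Week 24: 1 + 7 × 23 = 162. Week 12: 1 + 7 × 11 = 78. Both match Tables 2 and 3.
- On-schedule PegIFN start: 1 + 7 × (23 + 1) = 169 in Arm 1 and 1 + 7 × (11 + 1) = 85 in Arm 2.

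**Guaranteed relapse-free days under 4.1.3** = window end − start date, where window end = min(182 or 98, first PegIFN day). Arm 1 days are shown. Arm 2 gives the same results with 64, 78, 85, 92 and 98.

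| Response holds from | PegIFN on Day 169 | PegIFN on Day 176 | PegIFN on or after Day 182, or never |
|---|---|---|---|
| Day 148 (first window day) | 169 − 148 = 21 | 176 − 148 = 28 | 182 − 148 = 34 |
| Day 162 (planned visit) | 169 − 162 = 7 | 176 − 162 = 14 | 182 − 162 = 20 |
| Last day of window | 0 | 0 | 0 |

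For a participant responding from Day 148, PegIFN timing alone moves the figure by 34 − 21 = 13 days. The 4.1.3 origin can be 162 − 148 = 14 days before the planned visit. It can also fall after it, if response is first established later in the window.

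**Under 4.3.1.1** the first nominal visit that can count is Day 169 (Arm 1) or Day 85 (Arm 2), which is 7 days after the origin whatever the PegIFN start.

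**Arm 1 examples.** Protocol Tables 2, 4 and 5 schedule HBsAg and HBV DNA on the nominal days used here.
1. *Delayed PegIFN; below LLOQ on Days 148 to 176, first rise on Day 183.* Under 4.1.3, relapse is at 183 − 148 = 35 days. Under 4.3.1.1 it is at 183 − 162 = 21 days.
2. *Delayed PegIFN; below LLOQ to Day 162, at or above it on Days 169 and 176 and afterwards.* Under 4.1.3 the latest in-window value is non-response, so the participant is not in the cohort. Under a literal reading of 4.3.1.1, relapse is at 169 − 162 = 7 days.
3. *As example 2, but back below LLOQ on Day 176 and still so at window end.* Under 4.1.3 the participant stays in, with origin Day 176. Under a literal 4.3.1.1, relapse is at 7 days.

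An on-schedule starter is also affected, because the Day 169 sample falls on the last day of the window.

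**Threshold.** Response requires a value below LLOQ (SAP 4.2.2.1). A value equal to LLOQ therefore ends response, yet it is not a relapse under 4.1.3.1, which needs a value above LLOQ. It is a relapse under 4.3.1.1. Section 4.1.3.2 uses both operators.

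**The case against.** The strongest reply is that 4.3.1.1 offers only a general description of the rule detailed in 4.1.3, and that the strict inequality in 4.1.3.1 is a slip, since 4.2.2.2 and part of 4.1.3.2 use at or above LLOQ. The slip is likely. The first argument does not settle the matter: 4.3.1.1 has no cross-reference to 4.1.3, names a different origin and omits the window end. It is also fair to say that 4.3.1.1 restricts the cohort to end-of-bepirovirsen responders. If that status is taken from Tables 2 and 3, the participant in example 2 is excluded under both sections. The conflict over the denominator therefore depends on a literal reading of 4.3.1.1, but the text permits that reading.

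A reader might infer more than the documents support:
- *That late or never starters relapse earliest, so their durability is flattered.* No source is given. PegIFN ineligibility includes ALT at or above 5 × ULN (protocol 5.3). The protocol regards flares as therapeutic (4.2) and as correlated with falls in HBV DNA or HBsAg (8.3.7.1). Delayed starters could relapse later.
- *That every participant carries about 34 free days.* That is a maximum. It needs response from the first window day and PegIFN at least 13 days late or never given.
- *That the comparison between arms is biased.* Window lengths are the same in both arms, and the planned plot does not compare PegIFN-start groups.
- *That any rise after the planned visit removes the participant.* A transient rise need not, as example 3 shows.

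**Conclusion.** The two definitions are incompatible and no precedence is stated. Followed as written, 4.1.3 guarantees 21 to 34 relapse-free days for a participant responding from the first window day, 7 to 20 for one first responding at the planned visit, and less for later responders. These figures use nominal visit days with PegIFN starting on schedule or later. A start at the early edge of the 3-day visit window would lower the 21 to 18.

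The clock, numerator and denominator can all differ between the sections. The denominator difference arises for rises that persist to window end, with 4.3.1.1 read literally. The direction of any bias cannot be established from the documents. The arms are distorted differently only if PegIFN delay or response timing differs between them. The endpoint is descriptive and secondary, and primary SVR is unaffected. The point is still worth correcting, because the endpoint is meant to inform whether PegIFN delays relapse and the version history says it is analysed at the administrative interim analyses. An unresolved definition leaves room to choose one after results are seen.

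**What to change.** - **Relapse from bepirovirsen end of treatment.** Use one definition, cross-referenced between 4.1.3 and 4.3.1.1, with the same landmark for responder status, clock start and relapse eligibility. The landmark should not move with PegIFN start. One option is the planned Week 24/12 visit or, if that was missed, the last in-window assessment before it. Count relapse from the next visit onward. With the planned visit as landmark, the earliest nominal relapse is at 7 days for everyone.
- **Relapse from PegIFN end of treatment.** Section 4.1.3 also covers these responders, so keep a separate time zero for them at the planned Week 48/36 visit, on the same principle. Replacing the origin in 4.1.3 with Week 24/12 alone would leave this analysis without one.
- **Threshold.** Use at or above LLOQ throughout 4.1.3.1, 4.1.3.2 and 4.3.1.1, keeping the confirmation requirement in the modified definition.

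The cost is SAP wording and one re-derivation, with no new data. The downside is small: cohort counts may differ slightly from the windowed count of end-of-treatment responders, which a table footnote can explain.
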